13.2.2 Statistical Analysis of Pharmacokinetic Data

Step 1: Determine the Within-subject Standard Deviation of the Test and Reference Products (S_{WT} and S_{WR}) for the PK Parameters AUC_{72} , AUC_t , AUC_{inf} and C_{max} :

The within-subject standard deviation of the test and reference products will be determined for the ln-transformed PK parameters AUC_{72} , AUC_t , AUC_{inf} and C_{max} for tacrolimus.

For a fully replicated 4-way design with 2 sequences TRTR, RTRT, the within subject variance of the reference product, S_{WR}^2 can be determined as follows:

$$S_{WR}^2 = \frac{\sum_{i=1}^2 \sum_{j=1}^{n_i} (D_{ij} - \bar{D}_i)^2}{2(n-2)}$$

Where,

i = Number of sequences (2 used in the study),

j = Number of subjects within each sequence,

$D_{ij} = R_{ij1} - R_{ij2}$ (where R_{ij1} represents the first administered (early) reference and R_{ij2} represents the second administered (late) reference.)

$$\bar{D}_i = \frac{\sum_{j=1}^{n_i} D_{ij}}{n_i} \text{ (Mean within sequence } i \text{.)}$$

$n = \sum_{i=1}^2 n_i$ (total number of subjects used in the study, while n_i is the number of subjects used in sequence i .)

S_{WR} will be calculated as follows:

$$S_{WR} = \sqrt{S_{WR}^2}$$

The S_{WR} calculation will include subjects with estimated PK parameters for both reference administrations.

For a fully replicated 4-way design with 2 sequences TRTR, RTRT, the above method can be applied for the calculation of the within subject variance of the test product S_{WT} as well.

Step 2: Reference Scaled Average Bioequivalence Procedure

The 95% upper confidence bound for $(\mu_T - \mu_R)^2 - \theta S_{WR}^2$ will be determined for the ln-transformed PK parameters AUC_{72} , AUC_t , AUC_{inf} and C_{max} using a PROC MIXED model in SAS[®], where μ_T and μ_R are the means of the ln-transformed PK parameters obtained from the BE study for the test and reference products, respectively. θ is the scaled average bioequivalence limit defined as $\theta = \left(\frac{\ln(1/0.9)}{\sigma_{w0}}\right)^2$, where σ_{w0} is a regulatory constant which is set at 0.10.

The method of obtaining the upper confidence bound is based on *Howe's Approximation* [8]. The following steps will be followed to construct the 95% upper confidence bound.

- Let T_{ij1} , T_{ij2} , R_{ij1} and R_{ij2} be the log transformed observations on early test, late test, early reference and late reference for subject j within sequence i . Then we will calculate the following two terms:

- $I_{ij} = \frac{T_{ij1} + T_{ij2}}{2} - \frac{R_{ij1} + R_{ij2}}{2}$, and
- $D_{ij} = R_{ij1} - R_{ij2}$.

- Fit the Generalized linear mixed model (GLMM) with I_{ij} values as dependent variable. Sequence is the explanatory variable of the model. The confidence interval for the least squares mean of I will be estimated at 10% significance level. Let L and U be the lower and upper bounds of the confidence interval. Also the least squares mean of I will be calculated by determining the average of the 2 sequence means, using the ESTIMATE function of GLMM. Suppose Φ is the estimated least squares mean of I and $SE(\Phi)$ is the standard error of this estimate.

Calculate the following estimates:

$$\Delta_1 = \Phi^2 - SE(\Phi)^2$$

$$B_1 = (\max((\text{abs}(L)), (\text{abs}(U))))^2$$

- Fit the GLMM with D_{ij} values as the dependent variable. Sequence is the explanatory variable of the model. The within subject variance of the reference product, S_{WR}^2 , will be calculated as,

$$S_{WR}^2 = \frac{MSE}{2}$$

Where MSE is the mean square error from the model and let κ be the corresponding degrees of freedom.

4. Now the 95% upper confidence bound for $(\mu_T - \mu_R)^2 - \theta S_{WR}^2$ will be calculated as follows:

$$(\Delta_1 + \Delta_2) + \sqrt{(B_1 - \Delta_1)^2 + (B_2 - \Delta_2)^2}$$

Where,

$$\Delta_2 = -\theta S_{WR}^2$$

$$B_2 = \frac{\Delta_2 \kappa}{\chi_{\kappa, 0.95}^2}$$

$\chi_{\kappa, 0.95}^2$ is the chi-square tabulated values at 5% significance level.

Step 3: Unscaled Average Bioequivalence Procedure

The unscaled average bioequivalence analysis was performed using PROC MIXED in SAS[®], with SEQUENCE, PERIOD, and TREATMENT as fixed effects, TREATMENT and SUBJECT as random effects on the logarithm of the pharmacokinetic parameters (AUC₇₂, AUC_t, AUC_{inf} or C_{max}).

The following illustrates the program statements to run the ANOVA using PROC MIXED in SAS, with SEQ, SUBJ, PER, and TRT identifying sequence, subject, period, and treatment variables, respectively, and Y denoting the response measure (e.g., ln(AUC₇₂), ln(AUC_t), ln(AUC_{inf}), ln(C_{max})) being analyzed:

```
PROC MIXED;
  CLASSES SEQ SUBJ PER TRT;
  MODEL Y = SEQ PERTRT / DDFM=SATTERTH;
  RANDOM TRT/TYPE=FA0(2) SUB=SUBJ G;
  REPEATED/GRP=TRT SUB=SUBJ;
  ESTIMATE 'T vs. R' TRT 1 -1/CL ALPHA=0.1;
```

All the fixed effects will be tested using the Type 3 Tests of Fixed Effects in the ANOVA to detect statistically significant differences ($\alpha=0.05$).

The REPEATED statement in PROC MIXED is used to specify covariance structures for repeated measurements on subjects. Least squares means for the treatments and the adjusted difference between treatment means together with the associated standard error (σ_D) will be estimated in this procedure.

The two one-sided hypotheses [9] at the alpha level ($\alpha=0.05$) of significance will be tested by constructing the 90% confidence interval for the ratio between the test and reference means.

The same ANOVA using the linear mixed-effects model will be performed on the raw data for T_{max} , Lambda (or λ), and $T_{1/2}$ parameters.

Step 4: Calculate the 90% CI of the Ratio of the Within-subject Standard Deviation of Test Product to Reference Product (σ_{WT}/σ_{WR}).

The 90% CI for σ_{WT}/σ_{WR} is given by

$$\left(\frac{S_{WT}/S_{WR}}{F_{\alpha/2}(v_1, v_2)}, \frac{S_{WT}/S_{WR}}{F_{1-\alpha/2}(v_1, v_2)} \right)$$

where

- S_{WT} is the estimate of σ_{WT} with v_1 as the degree of freedom;
- S_{WR} is the estimate of σ_{WR} with v_2 as the degree of freedom;
- $F_{\alpha/2}(v_1, v_2)$ is the value of the F-distribution with v_1 (numerator) and v_2 (denominator) degrees of freedom that has the probability of $\alpha/2$ to its right
- $F_{1-\alpha/2}(v_1, v_2)$ is the value of the F-distribution with v_1 (numerator) and v_2 (denominator) degrees of freedom that has the probability of $1 - \alpha/2$ to its right
- here $\alpha = 0.1$.

Individual concentration at each scheduled time point and individual PK parameters will be listed by treatment. Two SAS transport files including xconc.xpt for individual concentration at each scheduled time point and xpara.xpt for individual PK parameters, as well as a Define.pdf file to describe each SAS transport file will be provided.

Descriptive statistics (including number of subjects (N), arithmetic mean, standard deviation (SD), minimum, maximum, median and coefficient of variation (CV%)) of concentrations will be presented by treatment at each scheduled time point.

Descriptive statistics (including N, arithmetic mean, SD, minimum, maximum, median and CV%) of all PK parameters will be presented by treatment.

The mean and individual concentration-time profiles will be plotted in linear and semi-logarithmic scales.

If the study is dosed in two or more groups of subjects, the statistical model will be modified to reflect the multi-group nature of the study.

Additional statistical and alternate tests will be performed if necessary.

Further details for statistical analysis of PK data will be described in the Statistical Analysis Plan (SAP).

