5.3 Randomization and Blinding

In this study, the assignment of treatment groups (simple randomization scheme) will be generated by a computer program designed and run in SAS[®] Version 9.4 [REDACTED]

Subjects who meet the eligibility criteria will be randomly assigned equally into one of the following two sequence groups:

Table 5-1 Randomization Scheme

	Period 1	Period 2	Period 3	Period 4
Sequence 1	T	R	T	R
Sequence 2	R	T	R	T

Each subject is scheduled to receive each treatment twice by the end of the study.

Treatment T (Test): 1 × 1mg tacrolimus capsules [REDACTED]

Treatment R (Reference): 1 × 1mg Prograf[®] 1 mg capsules [REDACTED]

Approximately 32 subjects are planned to receive treatment sequence T-R-T-R and approximately 32 subjects are planned to receive treatment sequence R-T-R-T.

The trial will be performed as an open-label study as the pharmacokinetic profile should not be expected to be affected by having the knowledge of whether reference or generic tacrolimus capsules were administered. Blinding of the subjects as well as clinic staff is not considered necessary. Only the bioanalytical laboratory staff will not have access to the randomization scheme until the bioanalytical analysis is complete.

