13.4 Bioequivalence Criteria [7, 10]

To establish bioequivalence, all the following conditions for individual PK parameter(s) AUC₇₂, and C_{max} must be met:

- The 90% CI for the Test/Reference ratios of geometric means are completely contained within 80.00%-125.00%.
- The 95% upper confidence bound for $(\mu_T - \mu_R)^2 - \theta S_{WR}^2$ should be less than or equal to 0.
- The upper limit of the 90% confidence interval for the Test/Reference ratio of the within-subject standard deviation (σ_{WT}/σ_{WR}) is less than or equal to 2.5.

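### Does the illustrative PROC MIXED contrast in Step 3 report Reference/Test instead of Test/Reference?

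*Combined protocol and SAP*

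**What the plan says.** Section 13.2.2, Step 3, sets out the unscaled average bioequivalence analysis. It introduces its code with the words "The following illustrates the program statements to run the ANOVA using PROC MIXED in SAS". The class statement is "CLASSES SEQ SUBJ PER TRT" and the contrast is "ESTIMATE 'T vs. R' TRT 1 -1/CL ALPHA=0.1". No ORDER option, format or stored values for TRT are given.

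Section 5.3 names the products by letter: "Treatment T (Test): 1 × 1mg tacrolimus capsules" and "Treatment R (Reference): 1 × 1mg Prograf".

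The direction of the result is fixed elsewhere. Section 13.4 says: "The 90% CI for the Test/Reference ratios of geometric means are completely contained within" 80.00% to 125.00%. The Synopsis states the same criterion. Step 2 of Section 13.2.2 defines its own contrast, I, as the mean of the two test values minus the mean of the two reference values. Section 13.2.2 also plans least squares means for each treatment, descriptive statistics of every PK parameter by treatment, and mean concentration-time plots. It leaves further analysis detail to the SAP.

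**The concern.** In an ESTIMATE statement the coefficients attach to the class levels in the order in which the procedure holds them. If that order is the sorted one, the letters T and R become R, T. The coefficients 1 and -1 then give ln(R) minus ln(T), although the label reads T vs. R.

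The consequence would be a report that points the wrong way. The geometric mean ratios and confidence intervals for AUC72, AUCt, AUCinf and Cmax would be inverted. The same model is run on untransformed Tmax, lambda and half-life, so those differences would change sign. Step 3 would also disagree in sign with the Step 2 mean of I.

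Direction has some importance in this study. Section 3.1 says the generic was chosen because earlier laboratory and preclinical work suggested it may not match the brand, and it describes conversion to crystalline drug as a route to lower exposure. A reader would want to know whether exposure to the generic is lower or higher.

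**Working it through.** The documents give no numerical result that depends on this line, so there is no figure to reproduce. The check has four parts.

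**1. Level order under plausible codings.** Assumption: class levels are sorted by value unless told otherwise. This is general knowledge of SAS and is not stated in the documents.

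| Stored values of TRT | Sorted order | 1 -1 gives |
|---|---|---|
| T, R | R, T | R minus T |
| Test, Reference | Reference, Test | R minus T |
| Tacrolimus, Prograf | Prograf, Tacrolimus | R minus T |
| 1 = Test, 2 = Reference | Test, Reference | T minus R |

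A format or ORDER setting that puts Test first also gives T minus R. The documents do not say which row applies.

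**2. Size of an inversion, if it happened.** The printed ratio is 1/(T/R), and the confidence limits swap:
- T/R = 0.90: 1/0.90 = 1.1111, printed as 111.1%.
- Limits 0.86 and 0.94: 1/0.94 = 1.0638 and 1/0.86 = 1.1628, printed as 106.4% to 116.3%.
- T/R = 0.95: 1/0.95 = 1.0526, printed as 105.3%.

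One simulated replicate data set (assumed 64 subjects, true T/R 0.90, within-subject SD 0.15) gave T/R = 91.39% (89.18% to 93.65%) in the intended direction and 109.42% (106.79% to 112.13%) in the other.

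**3. Effect on each bioequivalence criterion.**
- *Average bioequivalence limits.* ln(0.80) = -0.2231 and ln(1.25) = 0.2231. The interval is symmetric about zero on the log scale, so a confidence interval lies inside it exactly when its mirror image does. The level is also unaffected: two one-sided tests at 0.05 give a 1 - 2(0.05) = 90% interval, which agrees with ALPHA=0.1.
- *Scaled criterion.* It uses the separately defined I, not the Step 3 contrast. Even with the sign of I reversed, the squared mean, its standard error and the larger of |L| and |U| are unchanged. In the simulated data set the upper bound was -0.01143 in both directions.
- *Standard-deviation ratio.* It is built from S_WT and S_WR and does not use the ESTIMATE line.

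**4. Simulated decisions.** In 20,000 simulated trials (assumed within-subject SD 0.20, true T/R drawn from 0.76 to 1.32), the decision against 80.00% to 125.00% was compared in the two directions. It differed in 0 trials unrounded and in 1 trial after rounding the limits to two decimals. Rounding can matter only at the very edge: a lower limit of 79.996% rounds to 80.00% and passes, while its reciprocal, 100/0.79996 = 125.006%, rounds to 125.01% and fails.

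**The case for a change.** The best argument for a change runs as follows. The only codes the protocol gives the products are T and R, and three of the four codings above invert the contrast. This is the only program supplied for one of the required criteria. Step 3 is also the step that supplies the reported ratio, since the Step 2 bound squares the difference and carries no direction. No sign check is prespecified, and the remedy would take one line.

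Much of this is fair. The inversion is real under that coding, the coding is plausible, and the direction of any difference is of scientific interest here.

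The argument does not show an error in the plan, however. Section 5.3 labels the treatments; it does not specify a data set. The fragment names no data set and is offered as an illustration, so a missing ORDER option says little about the production program. Pairing the label T vs. R with 1 and -1 fits an author who had Test as the first level in mind. Whoever programs the analysis has an explicit target, Test over Reference. The planned output also makes a mistake visible: an inverted estimate would contradict the least squares means from the same procedure, the by-treatment summaries and the Step 2 mean of I.

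**Conclusion.** The concern does not call for a change. What is missing is the coding of one variable in an illustrative fragment, and an analyst settles that when programming the Test/Reference ratio that the plan requires.

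If the coding were T and R in sorted order and nobody compared the estimate with the treatment means, the four ratios would be inverted (90.0% shown as 111.1%) and three differences would change sign. No bioequivalence conclusion would change, apart from a rounding tie at a limit (1 of 20,000 simulated trials). The conclusion that the decision is unaffected rests on the reciprocal limits and the squared criterion, and needs no assumption about coding. The conclusion that an inversion would be noticed rests on the planned treatment means being produced and read. Writing down the level order of TRT in the programming specification is harmless good practice, but the plan is adequate without it.

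### The Step 4 interval for σ_WT/σ_WR divides by F instead of √F, so the third bioequivalence criterion is tested at about 99.9% confidence instead of 90% and can wrongly fail the product

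*Combined protocol and SAP*

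**What the plan says.** Section 13.2.2 has a step headed "Step 4: Calculate the 90% CI of the Ratio of the Within-subject Standard Deviation of Test Product to Reference Product", which introduces its formula with "The 90% CI for σ_{WT}/σ_{WR} is given by". The printed limits are S_WT/S_WR divided by F_{α/2}(v1, v2) and S_WT/S_WR divided by F_{1−α/2}(v1, v2), with α set to 0.1. There is no square root on F. The symbols are defined beneath the formula:

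- "S_{WT} is the estimate of σ_{WT} with v_1 as the degree of freedom", and S_WR likewise for the reference with v2.
- Each F term "is the value of the F-distribution with" v1 and v2 degrees of freedom. The first is the value with "degrees of freedom that has the probability of $\alpha/2$ to its right", the second the value with 1−α/2 to its right.

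Step 1 of the same section obtains S_WR as the square root of the within-subject variance and applies the same method to the test product. Both are therefore standard deviations.

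Section 13.4 (and the synopsis) makes the result decisive: "The upper limit of the 90% confidence interval for the Test/Reference ratio of the within-subject standard deviation" must be no more than 2.5, for AUC72 and for Cmax, along with two other conditions that must also be met.

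**The concern.** The numerator is on the SD scale and the divisor is on the variance-ratio scale. The printed expression is therefore a 90% interval neither for σ_WT/σ_WR nor for its square. For the planned sample sizes F_{α/2} is above 1 and F_{1−α/2} is below 1, so dividing by F rather than √F pushes both limits outward and makes the upper limit too high.

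Failing this one condition denies bioequivalence even when the mean comparison and the reference-scaled criterion are met. A product whose true 90% interval lies within the limit could be reported as not bioequivalent because of a formula error. The study is meant to inform review standards for narrow therapeutic index drugs (Section 3.2), so a false negative of this kind would mislead on the question being asked. Any interval reported as a 90% CI would also be mislabelled.

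**Working it through.** **Inputs.** α = 0.1 and the formula: Section 13.2.2, Step 4. Degrees of freedom n − 2 for each product: the divisor 2(n − 2) in Step 1. Sample sizes: about 64 dosed and at least 48 completing (Section 7.1), so v1 = v2 = 62 or 46. Limit 2.5: Section 13.4. Normality of the ln-transformed data is assumed, as the F method requires. Subscripts on F are right-tail probabilities, as in the protocol.

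**Correct interval.** Write r = S_WT/S_WR and ρ = σ_WT/σ_WR. Then r²/ρ² follows F(v1, v2), so

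P(F_{0.95} ≤ r²/ρ² ≤ F_{0.05}) = 0.90.

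Solving for ρ² gives r²/F_{0.05} to r²/F_{0.95}. Taking roots gives r/√F_{0.05} to r/√F_{0.95}.

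**Coverage of the printed interval.** The condition r/F_{0.05} ≤ ρ ≤ r/F_{0.95} is the same as F_{0.95}² ≤ r²/ρ² ≤ F_{0.05}². Its probability is P(F_{0.95}² ≤ F ≤ F_{0.05}²), which is not 0.90.

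| Quantity | n = 48 (df 46) | n = 64 (df 62) |
|---|---|---|
| F_{0.05} | 1.632 | 1.524 |
| F_{0.95} | 0.6126 | 0.6564 |
| √F_{0.95} | 0.7827 | 0.8102 |
| Two-sided coverage, printed | 99.88% | 99.89% |
| Two-sided coverage, √F | 90.0% | 90.0% |
| One-sided confidence of upper limit, printed (√F: 95%) | 99.94% | 99.94% |
| Upper-limit multiplier, printed vs √F | 1.632 vs 1.278 | 1.524 vs 1.234 |
| Largest r that passes 2.5, printed | 2.5 × 0.6126 = 1.53 | 2.5 × 0.6564 = 1.64 |
| Largest r that passes 2.5, √F | 2.5 × 0.7827 = 1.96 | 2.5 × 0.8102 = 2.03 |

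The plan's stated 90% is reproduced only with √F. The printed upper limit is too high by 1.632/1.278 − 1 = 28% at n = 48 and by 1.524/1.234 − 1 = 23% at n = 64. Simulation with 400,000 draws agreed with the exact coverage (99.89% at n = 48, 99.88% at n = 64). Unequal degrees of freedom (46/50, 50/46, 60/62) also gave coverage of 99.88% to 99.89%.

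**Worked case.** Take an observed SD ratio of 1.7 at n = 48. The printed upper limit is 1.7 × 1.632 = 2.77, which fails. The correct one is 1.7 × 1.278 = 2.17, which passes.

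**Chance of failing the criterion for one PK parameter.** This is 1 − P(F ≤ (c/ρ)²), where c is the largest passing r from the table. The documents give no value for ρ, so a range is shown.

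| True ρ | n = 48: printed vs √F | n = 64: printed vs √F |
|---|---|---|
| 1.0 | 0.2% vs <0.1% | 0.01% vs <0.01% |
| 1.25 | 8.6% vs 0.15% | 1.7% vs 0.01% |
| 1.5 | 44% vs 4% | 24% vs 1% |
| 1.6 | 62% vs 9% | 42% vs 3% |
| 1.75 | 82% vs 23% | 69% vs 13% |
| 2.5 | 99.94% vs 95% | 99.94% vs 95% |

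**All three criteria together, one parameter.** This simulation assumed a geometric mean ratio of 0.95, within-subject SDs of 0.20 (reference) and 0.30 (test), and no subject-by-formulation variance. The pass rate was 0.55 as printed against 0.95 with √F at n = 48, and 0.76 against 0.99 at n = 64. Section 13.4 needs both AUC72 and Cmax to pass, so these are not study-level probabilities.

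**The case against.** Five points can be made for the plan.

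- **A radical may have been lost when the PDF was read.** This cannot be excluded from the text alone, and the definitions of F would read the same under a radical. However, the root signs in Step 1 and in the Howe bound of Step 2 survived, which makes a loss here unlikely. The original page will settle it.
- **The analysis actually run may differ.** Section 13.2.2 defers further detail to a SAP, Section 13.2 allows justified changes, and Section 13.4 cites regulatory guidance for the criteria. The SAS code may therefore be right. But no square-root version appears in the documents reviewed, and the protocol formula would still be wrong.
- **The error is conservative.** This is correct. At a true ratio of 2.5 the pass rate is 0.06% instead of 5%, so it cannot help an unduly variable product through. The cost is false failure.
- **It hardly matters if the products are similarly variable.** This is also correct. At a true ratio of 1.0 the failure rate as printed is 0.2% at n = 48 and 0.01% at n = 64. In a simulation of all three criteria at n = 64 (geometric mean ratio 0.95, reference SD 0.20), pass rates were 0.9997 against 0.9998 at a ratio of 1.0, and 0.992 against 0.999 at 1.2.
- **Nothing predicts a more variable test product.** Section 3.1 raises doubts about the generic's performance, but through crystallisation and lower solubility, which bear on mean exposure. The documents do not say that higher within-subject variability is expected.

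These points limit how likely the error is to change this study's result. None of them makes the printed interval a 90% interval.

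**Conclusion.** The concern holds. By the protocol's own definitions the Step 4 formula is wrong: it yields an interval of about 99.9% coverage at every planned sample size, where 90% is stated. The mandatory criterion in Section 13.4 is consequently stricter than specified. It would wrongly fail an observed SD ratio between about 1.53 and 1.96 with 48 completers, or between about 1.64 and 2.03 with 64.

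The coverage and the thresholds rest only on normality and the planned numbers. The failure probabilities also rest on assumed true SD ratios. The effect becomes material when the test product is roughly 1.5 times as variable as the reference or more; with only 48 completers it is already visible at 1.25. Because the formula decides a required condition, it must be corrected before the analysis is run.

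**What to change.** In Section 13.2.2, Step 4, replace the limits with (S_WT/S_WR)/√F_{α/2}(v1, v2) and (S_WT/S_WR)/√F_{1−α/2}(v1, v2). Computing the interval for the variance ratio and taking square roots of both limits is equivalent. Keep α = 0.1 and the limit of 2.5. State v1 and v2 explicitly as the number of subjects with both administrations of the product concerned, minus 2.

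Check the original protocol page, any separate SAP text and the SAS program against this formula. The cost is one formula and one line of code; no design change or new data is needed.
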